approached to participate) in our previous studies.^{18,29,54} The project coordinator will assess the first eligibility criteria (number of household members, child <18 years-old in household and Spanish/English-speaking). If the household is eligible, the coordinator will ask who is the primary caregiver of the children in the household and then ask if that person has a cellphone with text messaging and if they are willing to be the household reporter, as well as confirm that they and the household are not planning on moving in the next year. If these criteria are met, a home visit for enrollment will be scheduled. The household reporter will provide written consent, which will include being the household reporter and sending and receiving text messages. Other household members will be provided with an information sheet in English or Spanish explaining the study and the request for self-swabs from both ill participants and asymptomatic participants. In our text message surveillance study, these procedures were approved by the Columbia University Medical Center Institutional Review Board. Each study participant will be given a unique study ID coded to their household. Multiple other sources of contact information, if available, will be collected for the household reporter including landline and email address.

Randomization Procedures. On study enrollment, we will randomize 400 households (100 from each community) 1:1 to surveillance + education vs. surveillance-only arm, stratified by community and sampling site. Randomization will be conducted by the programmer under the supervision of the study statistician using permuted blocks ensuring balance between the arms. The programmer will enter the study arm the household is randomized to into the text messaging platform database, but arm assignments will not be visible to other research staff. Thus, the statistician and research staff will be blinded to arm.

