All analyses will be based on randomized arm assignment (intention-to-treat). An ill person will be considered an ILI/ARI index case for a household if, at the onset of illness, no one else in the household had been symptomatic within the previous 5 days.²⁹ Non-index household members will be defined as secondary cases if they are confirmed by RT-PCR as influenza-positive on day 3 or day 5 swab (symptomatic or asymptomatic).¹⁶ Five days was selected based on our previous studies and the influenza incubation period.²⁹ The secondary attack rate will be defined as the number of secondary cases of laboratory-confirmed influenza (both symptomatic and asymptomatic) divided by the number of household members minus one (the index case). Secondary attack rates will be compared between the arms - surveillance plus education vs. surveillance-only - using chi square tests and a generalized linear mixed model (logistic regression for binary response, mixed model for clustering within a household). We will assess other co-variates in the models including for the index patient and household contacts: age, sex, vaccination status including vaccine type, antiviral use (treatment or prophylaxis), previous illness episodes reported for the household, influenza season and years in study.

Secondarily, we will assess the intervention's impact on additional outcomes using the same analyses as above: defining secondary cases based on (1) ILI-criteria (fever, cough, headache, sore throat, or myalgia) within 5 days of illness of index case; (2) ARI criteria (≥ 2 of a) rhinorrhea/nasal congestion; b) sore throat; c) cough; d) fever/feverishness; e) myalgia); (3) any laboratory-confirmed pathogen that is the same as the index case including non-influenza pathogens. An additional set of secondary outcome measures will be to assess the secondary attack rate at the household (cluster) level defined as the percentage of households with at least one secondary case as defined in the analyses above.

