We will use Pearson chi square to assess relationship between text message response rates and community, reporter's race/ethnicity, insurance and education. This will be defined as number of responses received per message sent. If more than one variable is significantly related to reporting rates ($p<0.1$), we will develop multivariable logistic models to assess this relationship. We will also assess response rates by arm.

SAMPLE SIZE AND POWER

We have based our sample size on the primary outcome. With 200 households per arm and an average of 3.8 persons/household, we will have 88% power to detect a decrease in secondary attack rates of laboratory-confirmed influenza from 12% (surveillance-only) to 5% (surveillance + education), based on type I error of 5% and an intracluster correlation coefficient of 0.29. The intracluster correlation, expected transmission rates for the surveillance-only arm, and effect size are derived from the paper by Cowling *et al.*, reporting a reduction from 12% to 5% between the hand hygiene and usual care arms in SAR when a non-text message based behavioral intervention was started at ≤ 36 hours of illness onset in the index case using laboratory-confirmed influenza as an outcome.¹⁶ In the MoSAIC study, secondary attack rates for laboratory-confirmed influenza have been 16.6% therefore an expected rate of 12% in the surveillance-only arm is conservative. We will also be powered for our secondary outcome; we will have 91% power to detect a decrease in symptomatic ILI/ARI from 23% to 11%.¹⁶ If we lose 80 households (20%) per season, we will still have at least 80% power to detect the decreases in both the primary and secondary outcome as above, even without household replacement.

POTENTIAL CHALLENGES AND SOLUTIONS Table 3

Challenge	Solution
1. Recruitment and retention	In our previous community studies retention was excellent. In our MoSAIC study, 75.9% of households recruited in year 1 were still in the study in year 3.
2. Non-representative sample	Since eligibility criteria include ≥ 3 members and ≥ 1 child, the sample will not be fully representative of the communities. However, the benefits of these inclusion criteria include higher likelihood of infection and transmission.
3. Reporting bias	3x/a week texting will decrease recall bias. We have shown under- and over-reporting to be low and confirmed the validity of household symptom self-reports.

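### The plan does not say whether the unadjusted chi-square or the household-clustered mixed model decides the primary comparison; if the chi-square decides, type I error is about 11-13%, not the stated 5%

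*Combined protocol and SAP*

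**What the plan says.** - **Unit of randomisation** (Randomization Procedures): "we will randomize 400 households (100 from each community) 1:1 to surveillance + education vs. surveillance-only arm".
- **Unit of analysis** (Statistical Plan, Aim): the secondary attack rate is the number of secondary cases "divided by the number of household members minus one (the index case"), so each contact is an observation.
- **Primary comparison** (same section): the arms are compared "using chi square tests and a generalized linear mixed model (logistic regression for binary response, mixed model for clustering within a household"). Neither method is named as primary, supportive or descriptive.
- **Secondary outcomes** (same section): the effect is assessed "on additional outcomes using the same analyses as above". These are ILI, ARI and same-pathogen infection among contacts. A further set is defined per household (at least one secondary case).
- **Sample Size and Power**: power is "based on type I error of 5% and an intracluster correlation coefficient of 0.29".
- **Exploratory Aim**: "We will use Pearson chi square to assess relationship between text message response rates and community" and the reporter's race/ethnicity, insurance and education. On the response rate: "This will be defined as number of responses received per message sent". If more than one factor has p<0.1, "we will develop multivariable logistic models to assess this relationship". No term for repeated messages from one reporter is mentioned, and response rates are also to be compared by arm.

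**The concern.** A chi-square on contacts treats members of one household as independent. The plan itself assumes that they are strongly correlated and that the arm is assigned to the household as a whole. The chi-square therefore understates the standard error and rejects too often. The mixed model does not have this fault, but both are listed for the same comparison with no rule between them. If the chi-square decides, or if success on either test counts, the trial does not run at its stated 5%. If the tests disagree, the choice would be made after seeing the results. Keeping analysts blind to arm labels does not settle which test counts.

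The household-level outcome has one observation per household in an episode, so it is free of this within-household problem.

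In the exploratory aim, community, race/ethnicity, insurance and education are fixed for each reporter while messages repeat many times. Chance differences between groups of reporters could then appear as significant differences and falsely contradict the hypothesis that response rates are similar.

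**Working it through.** **Inputs**
- From Sample Size and Power: 200 households per arm, 3.8 persons per household, rates of 12% and 5%, type I error 5% (sides not stated; two-sided assumed), ICC 0.29.
- From the attack-rate definition: 3.8 − 1 = 2.8 contacts per household.
- Variation in household size is not given (eligibility sets only a minimum of three people). Assumed coefficient of variation (CV) of contacts: 0 to 0.4.
- From the surveillance schedule: three messages a week, November to March, so 151/7 × 3 = 64.7 per reporter per season.
- Within-reporter ICC is not given. Assumed range: 0.01 to 0.30.

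**1. The stated power.** There are 200 × 2.8 = 560 contacts per arm. With design effect DE = 1 + (3.8 − 1) × 0.29 = 1.812, the effective number is 560/1.812 = 309.1 and the power is 87.9%, which reproduces the stated 88%. This uses 2.8 for the count but 3.8 in the design effect; with 2.8 in both, power is 92.7%. Ignoring clustering gives 98.8%. So the stated figure belongs to a test that allows for clustering.

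**2. Type I error of the unadjusted chi-square.** The formula is P(χ² > c/DE), where c is the nominal critical value and DE = 1 + ((1 + CV²) × m − 1) × ICC.
- Equal sizes, m = 2.8: DE = 1 + 1.8 × 0.29 = 1.522, giving 11.2%.
- CV 0.2 / 0.3 / 0.4: DE = 1.55 / 1.60 / 1.65, giving 11.6 / 12.1 / 12.7%.
- DE 1.812, as implied by the stated power: 14.5%. This rests on a cluster size of 3.8 rather than the 2.8 contacts analysed.
- Sensitivity with equal sizes: ICC 0.10 gives 7.1% and ICC 0.20 gives 9.3%.

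**3. Both tests on the same simulated data, no true effect.** Contacts were beta-binomial with ICC 0.29, 2 to 5 per household (mean 2.8). The mixed model was a random-intercept logistic model with arm as the only covariate, tested by likelihood ratio.

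| Attack rate, households per arm | Runs | Chi-square | Mixed model | Either | Chi-square only |
|---|---|---|---|---|---|
| 12%, 200 | 2000 | 11.0% | 4.3% | 11.0% | 6.7% |
| 12%, 100 | 1500 | 12.7% | 5.5% | 12.7% | 7.2% |
| 8.5%, 200 | 1500 | 13.1% | 5.6% | 13.1% | 7.5% |

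The Monte Carlo standard error is about 0.5 to 0.9 percentage points. A separate simulation with 10,000 runs per setting and 200 households per arm gave 10.7-12.9% for the chi-square and 4.8-5.0% for a cluster-robust test.

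**4. Response rates.** The same formula applies, with m = 64.7 and equal numbers of messages per reporter.

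| Assumed within-reporter ICC | DE | Two groups, nominal 5% | Four communities, nominal 5% |
|---|---|---|---|
| 0.01 | 1.64 | 13% | 19% |
| 0.05 | 4.19 | 34% | 60% |
| 0.10 | 7.37 | 47% | 79% |
| 0.20 | 13.74 | 60% | 90% |
| 0.30 | 20.11 | 66% | 94% |

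At the p<0.1 screen the ranges are 20-71% (two groups) and 28-96% (four communities).

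**The case against.** The strongest reply is that a valid analysis is already planned. The mixed model is named for this comparison, the sample size allows for clustering, and both the covariates and the indicator for replacement households are placed in the models. A natural reading is that the chi-square is the crude comparison and the mixed model carries the inference. The text can also be read as requiring both tests to be significant. In the simulations every mixed-model rejection was also a chi-square rejection, so that rule would hold the mixed model's 4.3-5.6%. This stands in part: clustering is not ignored, and what is missing is the hierarchy. But neither benign rule is written down, and the chi-square is listed first on an equal footing.

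Second, 11-13% is conditional. It rests on an ICC borrowed from a cited trial, on assumed variation in household size, and on one episode per household. That is correct. Still, 0.29 is the value the plan chose, and the error exceeds 5% at lower values too. Repeat episodes in the same household, if treated as independent, could raise it further.

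Third, naming the mixed model does not settle which covariates it contains, and the 5% was checked only for an arm-only model. That is true, but it is a separate matter.

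Fourth, the response-rate aim is exploratory, its figures rest entirely on assumed correlations, and false positives there would count against the investigators' own hypothesis. This is why it ranks lower.

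**Conclusion.** The concern holds and should be fixed before the arms are unmasked. The plan lists an unadjusted and a clustered test for one confirmatory comparison and does not say which decides. If the chi-square decides, or if either test is enough, type I error is about 11-13%, more than double the stated 5%. This assumes ICC 0.29, 2.8 contacts per household, a CV of contacts up to 0.4, and a two-sided test. If the mixed model decides, or both must pass, it is about 5%. The tests conflict, with the chi-square alone significant, in about 7% of trials with no effect. The individual-level secondary outcomes carry the same ambiguity.

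The response-rate analysis is the same kind of fault at lower severity. Its direction is clear, but its size cannot be fixed from the documents. Even an assumed within-reporter ICC of 0.01 gives 13% for two groups and 19% for four communities.

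**What to change.** In the Statistical Plan, state that the household-clustered mixed model, or an equivalent cluster-adjusted test, is the sole test of the primary outcome. Make the chi-square descriptive or adjust it for clustering, and say the same for the individual-level secondary outcomes.

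For response rates, including the comparison by arm, either analyse one proportion per household or fit a logistic GEE or mixed model clustered on household. Report group differences with 95% confidence intervals, so that similarity is judged from the interval and not from a non-significant p-value.

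The cost is one sentence for the primary analysis and a different SAS procedure for response rates. Intervals will be wider than the unadjusted ones. No stated power is lost, since the 88% already includes the ICC.

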We will enroll and randomize 400 households (n=~1500 individuals) with ≥ 1 child recruited from four contiguous communities in New York City 1:1, stratified by community, to receive surveillance-only vs. surveillance plus text message educational intervention. We will have 88% power to detect a decrease in influenza SAR from 12% to 5%. These percentages are derived from the paper by Cowling *et al.*, reporting a reduction from 12% to 5% between hand hygiene and usual care arms in SAR for influenza when a non-text message-based behavioral intervention was started ≤ 36 hours of index illness onset.¹⁶ For surveillance, households in both arms will receive text messages 3x/week during each influenza season (Nov-Mar) and report household members with ILI/ARI symptoms. For those in the educational intervention arm, when an ILI/ARI is reported, educational text messages will be sent targeted to decrease household transmission.

Both arms will obtain one self-swab of the index case, and self-swabs of all other household members on days 3 and 5 from index onset.^{7,10,13,24} Swabs will be returned via postage-paid envelope and analyzed using an FDA-approved reverse-transcriptase multiplex PCR assay to identify influenza, including sub-types, as well as other viral respiratory pathogens, e.g., parainfluenza etc. We will also collect symptom reports from all household members. The primary outcome will be SAR of laboratory-confirmed influenza. Secondarily, we will assess SAR based on ILI/ARI symptoms, and of non-influenza viruses. Response rates will be compared between arms and by demographic factors (age, education, race/ethnicity). Trial results could provide support for text-based strategies to reduce influenza transmission.

B. RESEARCH STRATEGY

SIGNIFICANCE

Impact of Influenza: Influenza infection results in an estimated 31 million outpatient visits, 55,000 to 974,200 hospitalizations (2014-15 estimate: 974,206), and 3000 to 49,000 deaths (2014-15 estimate: 49,006) annually.¹⁻³ The burden of influenza also includes high cost from direct medical expenses, days lost from work or school,²⁵ and inappropriate use of antibiotics.²⁶ Children and adolescents 6 months-18 years old are at increased risk of influenza morbidity and mortality, and influenza is one of the most common causes of hospitalization for the pediatric population.¹ School-aged children and adolescents also serve as an important reservoir, transmitting influenza to household members.^{1,27}

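### The primary analysis does not commit to adjusting for the randomisation strata. In the household-clustered model this is safe but slightly inefficient; the plain chi-square has a separate and larger problem.

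*Combined protocol and SAP*

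**What the plan says.** Randomization Procedures: "we will randomize 400 households (100 from each community) 1:1", with allocation "stratified by community and sampling site", carried out "using permuted blocks ensuring balance between the arms". The Specific Aims describe the same allocation as "stratified by community, to receive surveillance-only vs. surveillance plus text message educational intervention", with no mention of sampling site.

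Statistical Plan, Aim: the arms are compared "using chi square tests and a generalized linear mixed model (logistic regression for binary response, mixed model for clustering within a household". The household is the only clustering level named. The next sentence begins "We will assess other co-variates in the models including for the index patient and household contacts: age, sex, vaccination status" and goes on to vaccine type, antiviral use, previous illness episodes, influenza season and years in study. The attrition paragraph adds an indicator for replacement households.

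Community enters an analysis only in the exploratory comparison of text-message response rates. Sampling site enters none.

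The community factor is also not fixed. Study Setting and Population describes five areas: Washington Heights/Inwood, Central Harlem, East Harlem, West Harlem with Hamilton and Morningside Heights, and the Upper West Side with Lincoln Square. The Specific Aims, Randomization Procedures and Pretesting count four communities. Pretesting refers to a single Harlem area, which suggests that two areas were merged, but no text says so.

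**The concern.** Blocking within strata takes between-stratum variation out of the arm contrast. An analysis without the strata puts that variation back into the estimated standard error, which is then too large for the design actually used.

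The plan gives some reason to expect differences between strata. The areas are described as mostly Latino, mostly Black or mostly White. Recruitment runs through Head Start, clinics, private practices, social services and a church. The Significance section says crowding may raise risk in low-income households. None of this is an attack rate by stratum, so the size of any difference is unknown.

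At stake are a little precision and a pre-specification gap: whether the design factors enter the model is left to be decided after the data are seen.

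**Working it through.** **Inputs from the plan (Sample Size and Power; Statistical Plan).** 200 households per arm; 3.8 persons per household, so 2.8 contacts once the index case is removed; rates 12% and 5%; ICC 0.29; type I error 5%, taken as two-sided.

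**The plan's own power.** Contacts per arm: 200 × 2.8 = 560. The stated 88% reproduces with a design effect based on 3.8 persons: 1 + 2.8 × 0.29 = 1.812; 560/1.812 = 309; power 87.9%. With 160 households per arm the effective size is 247 and power is 79.9%. With the cluster size set to the 2.8 contacts, the design effect is 1 + 1.8 × 0.29 = 1.522, the effective size is 368 and power is 92.7%. No version contains a stratification term, so the fix changes no stated figure.

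**Clustered model, by formula.** If strata explain a share R² of the variance of household means, omitting them widens the interval by 1/√(1 − R²) − 1, and the true type I error is 2[1 − Φ(1.96/√(1 − R²))]. R² is an assumption, and the result depends on which variance it refers to. The ICC component is 0.29/(0.29 + 0.71/2.8) = 53% of household-mean variance. If R² is a share of that component only, it must be multiplied by 0.53.

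| Assumed R² | Share of household-mean variance: excess width, type I error | Share of ICC component: excess width, type I error |
|---|---|---|
| 2% | 1.0%, 4.8% | 0.5%, 4.9% |
| 5% | 2.6%, 4.4% | 1.4%, 4.7% |
| 10% | 5.4%, 3.9% | 2.8%, 4.4% |

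For scale, household-mean variance at a 12% rate is 0.12 × 0.88 × (0.29 + 0.71/2.8) = 0.0574. R² = 2% of it needs a between-stratum SD of √(0.02 × 0.0574) = 3.4 percentage points; R² = 10% needs 7.6 points.

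**Clustered model, by simulation.** 400 households, mean 2.8 contacts, beta-binomial ICC 0.29, balanced allocation within four strata, risk difference with household-robust SE, 8,000 runs per scenario. Each pair is without, then with, stratum terms.

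| Assumed control rates | Mean null SE | SE too wide by | Type I error | Power |
|---|---|---|---|---|
| all 12% | 0.0244, 0.0243 | none | 4.8%, 4.8% | 92.7%, 92.8% |
| 8% to 17% | 0.0245, 0.0242 | 1.0% | 4.9%, 5.1% | 92.6%, 93.0% |
| 6% to 20% | 0.0247, 0.0241 | 2.5% | 4.7%, 5.1% | 92.4%, 92.9% |
| 3% to 25% | 0.0250, 0.0235 | 6.3% | 3.8%, 5.0% | 92.4%, 93.7% |

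The Monte Carlo standard error of a 5% rejection rate is √(0.05 × 0.95/8,000) = 0.24 points, so only the last type I error departs clearly from 5%. Twenty strata (3,000 runs) gave a similar picture: SE about 2% and 5% too wide, and unadjusted type I error 4.7% and 3.7%, under moderate and strong spread. A deliberately extreme spread over 20 strata (1.9% to 36.3%) reached about 10%; I leave it out of the working range. With 20 strata and no spread, both analyses rejected at about 6%, so that excess does not come from omitting strata.

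**Plain chi-square.** It treats contacts as independent. With a design effect of 1.522, its true type I error is 2[1 − Φ(1.96/√1.522)] = 2[1 − Φ(1.59)] = 11.2%. The four-stratum simulations gave 10.9% to 12.0%.

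**The case against.** The strongest reply is that the plan is silent and has not ruled the strata out. The covariate list is introduced as a set of examples, so a reader who infers a decision to leave out community and site goes beyond the text. That stands: the defect is the absence of a commitment. An open list with no inclusion rule does not supply one.

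Second, the effect is small and in the safe direction. That also stands for the clustered model. A reader might infer that ignoring the stratified design makes the trial's inference invalid; the calculations do not support this.

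Third, blocking balances the households randomised, whereas the informative ones have an influenza-positive index case, a later subset that blocking does not balance exactly. If only a fraction f contributes (an assumption), roughly f × R² is removed by design. With R² = 10% of household-mean variance, type I error is then about 4.8% at f = 0.2 and 4.4% at f = 0.5, rather than 3.9%. This weakens the conservatism. Adjustment would still guard against chance imbalance in that subset.

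Fourth, the Specific Aims may simply summarise the fuller procedure. That is plausible, but both statements are current and a programmer needs one of them.

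A further tempting inference is that the chi-square, being unstratified, is conservative too. It is not: the unmodelled household clustering outweighs any conservatism from the strata.

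**Conclusion.** The point holds as a modest matter of efficiency and pre-specification. In the household-clustered model, leaving out the strata makes the standard error roughly 0.5% to 6% too wide, leaves type I error at or somewhat below 5%, and costs about 0.4 to 1.3 points of power. If attack rates do not differ between strata, it costs nothing. Validity is not threatened in that model.

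These figures rest on assumed between-stratum spreads, because the plan gives no attack rates by community or site. They also use a risk-difference model with robust errors in place of the logistic mixed model, where the gain would show mainly as power and less as a narrower odds-ratio interval. They further take every household as contributing contacts, as the plan's power calculation does.

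The plain chi-square must be judged separately. At the plan's own ICC its type I error is about 11%, because it ignores household clustering; adding strata alone would not repair it.

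**What to change.** - Name the household-clustered logistic mixed model as the primary test, in place of the plain chi-square.
- Pre-specify community as a fixed effect and sampling site as a random effect in that model, with a rule for pooling sparse sites and a rule for the site assigned to households recruited by snowball sampling.
- Reconcile the Specific Aims with Randomization Procedures on the stratification factors.
- Reconcile the five areas in Study Setting and Population with the four communities elsewhere, so that the model uses the same community variable as the randomisation.

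The cost is a short SAP amendment and a few extra model terms. Both factors must already exist at randomisation, so no new data are needed beyond the snowball rule. The number of sites is not stated and events may be few, so site terms could be unstable; the random effect or pooling deals with that.
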